Title: EFFECT OF MONOCHROMATIC LIGHT ON THE INCIDENCE OF EMERGENCE DELIRIUM IN CHILDREN; A SINGLE BLINDED RANDOMIZED CONTROLLED TRIAL

Protocol ID#: H-39878

Drafted 9/8/17

IRB submit 8/15/17

Collaborators:

[name], MS- Principle Investigator

[name], MBA, FAAP

Background:

Emergence delirium/emergence agitation (ED/EA) is a behavioral phenomenon of unclear etiology consisting of short lived behavioral changes that can be both traumatic to families and pose a safety risk to patients and staff. ED is characterized by a variety of presentations, including crying, excitation and agitation, that occur during the early stage of recovery from general anesthesia, generally in the first 30 minutes.

Involuntary activity in the bed and even thrashing about during an episode of ED can lead to dislodgement of IV cannulas, surgical dressings and or surgically placed items such as drains and catheters.

Emergence delirium occurs in children of all ages following an anesthetic with halogenated agents (e.g. sevoflurane/isoflurane) with or without having undergone a surgical procedure (e.g. MRI patients). Electroencephalograms (EEG) in patients experiencing emergence delirium show diffuse background slowing. Presently, the treatment for ED is to revert the patient back to a hypnotic state mainly with sedatives so that they may “reset” themselves postulating that by re-inducing a hypnotic state, the brain has time to resolve this issue. The hypothesis of this study is that during ED, there is failure of organized EEG activity, especially alpha wave activity and that by enhancing alpha activity, the incidence of ED may be reduced without the need for additional pharmaceuticals which may be costly, delay recovery and are not without adverse effects specifically cardiopulmonary depression.

Monochromatic light (ML) has been used in a variety of clinical and non-clinical applications to affect a variety of changes. Exposure to light of short wavelength within the visible spectrum (450-470nm) has been associated with effects on circadian rhythm, neuroendocrine and neurobehavioral changes and enhanced cognitive performance. Blue ML has been studied safely to enhance work-place alertness and productivity. Clinically, blue ML has been used safely for decades in the neonatal intensive care unit to treat jaundice.

Blue ML, has been known to suppress melatonin secretion and enhance alertness and workplace performance. The effect occurs within the retinal photoreceptive ganglion cells which mediate

the observed responses. The effect is even present in visually blind persons lacking outer retinal function. Short exposure to bursts of blue light has revealed enhanced neural activity on functional MRI. Use of blue ML has been shown to enhance EEG activity in the alpha range (awake range) compared with light of greater wavelengths. If using blue ML in the operating room may enhance alpha EEG activity, (a circadian marker for alertness) it may be possible to reduce the incidence of emergence delirium in the post-operative period and therefore the amount of (non-pain) sedative medication needed in recovery.

Purpose:

Emergence delirium is associated with a safety risk to patients and staff members in the fact that these children are uncontrollable and often thrashing which may result in self-inflicted injury (falls and collision with bedframe) or perturbation of intravenous or surgically placed devices. At present, the treatment involves re-sedating these patients (e.g. propofol or dexmedetomidine). These medications are certainly not without risk. If intravenous access has been lost, intra-nasal or intra-muscular administration of medications can be dangerous or impractical to administer at times of delirium.

The primary aim of this study is to ascertain if perioperative exposure to non-invasive monochromatic blue light can reduce the incidence of emergence delirium.

The secondary aim involves assessing the need for rescue interventions (e.g. hypnotic agents – propofol or dexmedetomidine).

Protocol/Risk/Subjects:

Patient identification

Patients ages 2-6 years undergoing routine tonsillectomy and adenoidectomy requiring general anesthesia would be identified for inclusion. Exclusion criteria would include: American Society of Anesthesiology classification other than 1,2; history of migraine headaches, ocular disorders, seizure history, psychiatric conditions, parental refusal, developmental delay and those patients on medication for attention deficit disorders or caffeine stimulants. Patients with contraindications to receiving inhalation agents, use of premedication with midazolam or dexmedetomidine would also be excluded.

Randomization

After enrollment and consent, each patient will be randomized to either placebo or intervention group. 110 sealed envelopes randomizing patients to the exposure group A (monochromatic light) or bulb B (placebo) white light bulb with blue outer coating.

The machine used for the study will be the Drager Photo-Therapy 4000 currently in use through the NICU at Texas Children's Hospital. The bulb is the standard Drager approved Osram Dulux 18W/830 commercially available bulb. This bulb produced light of 450-470nm wavelength, well within the visible spectrum. The protective plexi shield will remain in place. The bulb for the placebo group contains white florescent bulbs Osram Dulux 18W/830 with a blue plastic covering that will produce light containing all wavelengths in the visible spectrum but will appear blue due to the outer cover. To ensure that this bulb does not produce any monochromatic light, a calibration meter, (Solarmeter Model 9.4 Blue Light Meter measuring 422-499nm with range from 0-199.9 mW/cm² Blue Light) will be used.

Patients will be evaluated for emergence delirium by two nurses blinded to the study arm.

Each patient will be given a study specific number for de-identification of data avoiding use of any identifiers (name, DOB, MRN, date of service etc.).

Anesthetic Description

A standard and routine anesthetic will ensue for these patients in line with routine operative practices at Texas Children's Hospital, including an inhalational induction (mask) using sevoflurane 8%v/v with oxygen/nitrous oxide 3/7 L/min respectively, followed by intravenous cannula placement. Propofol will be administered if needed to facilitate oral endotracheal intubation at the discretion of the anesthesia attending. Dexamethasone (0.5mg/kg), ondansetron (0.1mg/kg) and morphine (0.1-0.2mg/kg) will be administered for anti-inflammatory, antiemetic and analgesic effects respectively. Intravenous fluid (lactated ringer solution) will be continuously infused with the appropriate volume to be determined by the anesthesia provider. Maintenance of anesthesia will be with sevoflurane with the concentration titrated to maintain an appropriate level of hypnosis as determined by the anesthesia provider. At the conclusion of the surgery, the patient will undergo routine deep extubation according to the routine practice of the anesthesia providers of record. On arrival to the PACU, the Drager phototherapy lamp will be illuminated over the patient's head and neck. Randomization will determine if the patient will be exposed to ML blue light or the placebo bulb (white bulb with blue over coating). The PACU staff and the anesthesiologist will be blinded to study arm. The placebo bulb will provide blue light of all wavelengths as to not compromise blinding. The light will remain active and over the patient until the patient has been in the post anesthesia recovery unit (PACU) for 30 minutes.

Postoperative evaluation for emergence delirium

Two PACU nurses blinded to the patient group will be asked to complete the PAED scoring scale for evaluation of emergence delirium. They will be asked to complete the scoring evaluation upon arrival to the PACU and at 10 minutes, 20 minutes and 30 minutes following arrival. Two nursing evaluations will be used to reduce inter-observer bias. A patient

experiencing emergence delirium will receive standard pharmacologic treatment as determined by the anesthesiology provider irrespective of study participation. Blinding of the nurse and anesthesia team will help to ensure that the nursing staff will call the anesthesia providers with any and all usual questions and the anesthesia provider to react and treat potential ED as per usual practice without being biased by the study.

The study will end at this point without the need for additional follow-up or patient contact related to the study.

Statistical Analysis Plan

Sample size/Data Analysis:

The PAED behavioral scale will be used to assess the incidence of emergence delirium. The PAED scale is a reliable tool to measure ED and involves five items: eye contact, purposeful actions, awareness of the surroundings, restlessness, and inconsolability. While other scales exist, the PAED scale is the standard for assessment of ED and is the only validated scale. A PAED score of >12 will be used to define ED.

Cohort means and standard deviations (SD) or counts and frequencies as appropriate for the variables collected. We will compare the blue light and Sham groups using the Student's t-test for continuous variables (e.g., age, PAED score) and the chi-square test for categorical variables (e.g. % female, ASA category). For counts < 5, the Fisher's exact test will be used. For baseline comparisons, absolute standardized differences instead of p-values will be used to compare the groups.

Given the prospective collection of data, missing data for the PAED scores over time indicated a patient woke up or experienced emergence delirium and so no imputation will be performed. To adjust for any remaining confounding among the variables collected, a logistic regression model with the outcome being emergence delirium and a second logistic regression model with the outcome being either ED or the patient had a PAED score of 12 or more at time periods 10, 20, and 30 min. Both regression models used as independent predictors the following variables: treatment group, age, weight, gender, and ASA category. Robust standard errors were derived to account for any within-cluster correlation at the individual nurse level given the possible serial correlation of outcomes within each nurse caring for his or her patients.

An a priori calculation of sample size was done using an incidence of 40% of emergence delirium in similar patient population. We assumed an absolute reduction of 25% (ie, 40% to 15%) in incidence of emergence delirium to be clinically significant. To detect this difference at 80% power with a two-sided alpha of 0.05, required a sample size of 98 participants.

All p-values < 0.05 were considered statistically significant.

Risk/Discomfort:

The study procedure poses no additional risk to patients. The major risk is loss of confidentiality.

Use of monochromatic light has been safely tested in numerous human studies and used routinely in the NICU without identified patient risk using the same Drager machines at TCH. The moment the patient is awake and making purposeful eye contact with the PACU RN, the lights will be terminated. The risk of phototherapy is well known from nearly 40 years of clinical use in neonates. The risk of phototherapy is predominantly in neonates, especially preterm infants with jaundice, all requiring prolonged and continuous exposure to high intensity light for many days. This study will not include any neonates (with immature retina) or long term exposure of >30 min. The study will be terminated the moment the patient is awake and making purposeful eye contact with the PACU RN to avoid unnecessary discomfort.

Benefits:

The study benefits include improved understanding of emergence delirium and potential for both reduction in the incidence of emergence delirium and the use of pharmacologic agents.

Consent procedures:

The parental or legal guardian permission form will be signed prior to the beginning of surgery.

Confidentiality:

Personal Health Information(PHI) will be safeguarded at all times. Patients will be assigned a study ID number; their name or other identifying information will not be used in any presentations or publications resulting from this research. Data will be kept in a locked office to which only departmental personnel have access. Data files will be stored on a secure hospital network drive.

Sample collection:

Patients will be enrolled prospectively and randomized to either study or placebo arms. In addition, each patient will be assigned a random non-identifiable study number to ensure anonymity.

The following information will be recorded:

Age in months, gender, duration of procedure, duration from induction to extubation, Recovery time (defined as arrival in PACU to first spontaneous eye opening or response to verbal command)

PAED behavioral scoring sheet will be completed at: (T=0 on PACU arrival, 10, 20 and 30 minutes post PACU arrival). Nurse determination of occurrence of ED.

Administration of supplemental dexmedetomidine, propofol, opioid or benzodiazepine in PACU will be noted if given. Opioid given to treat pain will be noted as such.

References:

Sikich N, Lerman J: Development and psychometric evaluation of the Pediatric Anesthesia Emergence Delirium Scale. *Anesthesiology* 2004; 100:1138-45.

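### One bulb model is named for both the active and the sham lamp, and the only light check, a single-band reading of the sham alone, cannot show how the two lamps differ in blue light

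*Combined protocol and SAP*

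**What the plan says.** The lamps are specified by model in one place only, the Randomization section of the protocol.

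- **Active lamp.** The machine is a Drager phototherapy unit already used in the hospital's neonatal unit. "The bulb is the standard Drager approved Osram Dulux 18W/830 commercially available bulb". The next sentence gives its output: "This bulb produced light of 450-470nm wavelength, well within the visible spectrum".
- **Sham lamp.** "The bulb for the placebo group contains white florescent bulbs Osram Dulux 18W/830 with a blue plastic covering". It "will produce light containing all wavelengths in the visible spectrum but will appear blue due to the outer cover".
- **Light check.** "To ensure that this bulb does not produce any monochromatic light, a calibration meter" will be used. The instrument is described as "Solarmeter Model 9.4 Blue Light Meter measuring 422-499nm with range from 0-199.9", in mW/cm².

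The Anesthetic Description section repeats the contrast as monochromatic blue light against a white bulb with a blue coating, and gives no model for either. Of the sham it says: "The placebo bulb will provide blue light of all wavelengths as to not compromise blinding".

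No section gives an irradiance for either lamp, a measuring distance, a time for the check, an acceptable reading, or what happens if the check fails. No measurement of the active lamp is described.

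**The concern.** The intervention in this trial is a light spectrum, so the lamp specification is the treatment definition. As written, it gives one product two incompatible emissions.

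The light check is the only step that could show what the two arms receive, and it has two gaps. It targets a property that the named instrument does not measure, and it leaves out the active lamp, so there is nothing to compare the sham with.

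This matters on the plan's own rationale. The Background attributes the biological effects to visible light of 450-470 nm, and reports that blue light raised alpha activity relative to longer wavelengths. A sham that emits all visible wavelengths includes that band by description. How much it delivers relative to the active lamp bears directly on how a finding of no difference should be read, and nothing in the protocol measures it.

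**Working it through.** The check is mainly a comparison of texts.

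1. **The two bulb entries.**

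| | Active lamp | Sham lamp |
|---|---|---|
| Model | Osram Dulux 18W/830 | Osram Dulux 18W/830 |
| Stated emission | 450-470 nm | all visible wavelengths |
| Added filter | none named beyond the plexi shield | blue plastic cover |

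 The cover does not explain the difference. The 450-470 nm output is attributed to the active bulb itself, and the sham is said to emit all wavelengths with its cover on. The two rows cannot both be right. No other section supplies a second model, so the documents do not show which entry is wrong.

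2. **Which lamp is checked.** The sentence about the meter follows directly on the description of the placebo bulb. Its aim, the absence of monochromatic light, makes sense only for the sham, because monochromatic light is what the active lamp is meant to give.

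3. **What the meter can show.** The meter covers one band, 422-499 nm, which is 499 − 422 = 77 nm wide. The active emission is stated as 450-470 nm, which is 470 − 450 = 20 nm wide and lies wholly inside that band. The meter returns one number in mW/cm² for the whole band. A 20 nm source and filtered broadband light could give the same number. The reading is therefore an amount of in-band light and says nothing about spectral width.

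4. **What a zero would mean.** A reading of zero would indicate no detectable blue light in the band. But the sham is described, in both Randomization and Anesthetic Description, as giving all wavelengths, so a reading above zero is expected. Taken literally as a demand for zero, the check would contradict the sham's own specification. Taken any other way, it has no stated limit.

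5. **The plan's own figure.** The Sample size/Data Analysis section gives 98 participants for 40% versus 15%, 80% power, two-sided alpha 0.05. With pooled variance under the null, no continuity correction and equal arms (assumed, since the ratio is not stated):

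 n per arm = [1.960 × √(2 × 0.275 × 0.725) + 0.842 × √(0.40 × 0.60 + 0.15 × 0.85)]² / 0.25² = 48.88, rounded up to 49, so 98 in total.

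 The figure reproduces. It does not measure the lamp problem and is not part of the point.

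6. **Size of any bias.** This would need the irradiance of each lamp and a relation between irradiance and incidence of delirium. The documents give neither, so no dilution or loss of power is computed.

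**The case against.** The strongest reply is that the duplicated model is a slip with little practical consequence. The active bulb is called the manufacturer's standard bulb, in a machine in routine neonatal use, and Risk/Discomfort repeats that the same machines are used there. Randomization and Anesthetic Description both set monochromatic light against a white bulb under a blue cover. This stands as to intent: the intended active lamp can be identified. A reader might infer from the shared model number that both arms received the same lamp, and the documents do not support that. What remains is an error in the only text that specifies the intervention by model.

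A second reply is that the wording about monochromatic light is loose, and that the meter does measure the useful quantity, the sham's in-band output. This also stands in part. The instrument is suitable for comparing the lamps; what is missing is the active lamp as comparator and an aim that the instrument can serve. As written, the check does neither job.

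Three further inferences should be resisted:

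- **That a light-emitting sham must bias toward no difference.** This holds only if the sham acts like the active lamp. Risk/Discomfort ends exposure at waking to avoid discomfort, so the plan itself allows that light may be unpleasant. A sham that increased agitation would push the other way.
- **That the 40% control rate assumes an inert sham, so the trial is underpowered.** The sample-size text says only that 40% comes from a similar population. It says nothing about the sham.
- **That a blue-looking sham is itself a flaw.** It is disclosed, and it is a defensible way to protect blinding.

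**Conclusion.** The point holds in two limited parts and should be fixed. First, the protocol contradicts itself on the bulb model, and at least one entry is wrong. This rests on the text alone. Second, the only light check cannot establish the property it names, and it does not show how the arms differ in blue-band light. This rests on reading the check as applying to the sham, which is the only sensible reading, and on the protocol's own description of the meter as a single-band instrument.

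The consequence is conditional. If the sham's in-band light acts as the active lamp's does, the contrast is diluted and a null result is hard to interpret. The documents give no basis for saying how likely or how large that would be. The sample size is not in error.

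**What to change.** 1. Reconcile the two bulb entries in the Randomization section, so that each lamp has its own model and its manufacturer-stated emission. The emission data must come from the manufacturer, because the meter cannot verify a spectrum.
2. Replace the check for monochromatic light with 422-499 nm readings of both lamps, using the meter already named, at the patient's head distance and with the plexi shield in place. Take them before enrolment and after any change of bulb or cover. The person taking them should neither score PAED nor treat the patients. Report both readings with the results.
3. If the sham's in-band output proves to be a material share of the active lamp's, keep the sham for blinding and word the conclusion as a comparison of narrow-band with broadband blue-filtered light. The documents give no dose-response, so what counts as material is a judgement to be stated with its reason. A numerical limit fixed in advance has no basis in the documents and is not required.

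The cost is a wording correction, emission data for each bulb, and a few readings with equipment already planned. The drawbacks are that one unblinded person must take the readings, and that the conclusion may have to be narrower.

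### Emergence delirium (ED), the primary outcome, is not fully defined: unscored children get no ED status, the nurse determination has no role, and no rule combines two nurses and four times

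*Combined protocol and SAP*

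**What the plan says.** - **Definition.** Under Sample size/Data Analysis in the Statistical Analysis Plan: "A PAED score of >12 will be used to define ED". No time point, rater or summary is attached to the cut-off.
- **Missing scores.** Same section: "missing data for the PAED scores over time indicated a patient woke up or experienced emergence delirium and so no imputation will be performed".
- **Scores collected.** Under Postoperative evaluation for emergence delirium, two blinded nurses are to "complete the scoring evaluation upon arrival to the PACU and at 10 minutes, 20 minutes and 30 minutes following arrival". That is up to 2 × 4 = 8 scores per child. The stated purpose of having two nurses is to limit observer bias; no combining rule is given.
- **Separate judgement.** Sample collection also lists "Nurse determination of occurrence of ED", without relating it to the PAED cut-off.
- **Second model.** Its outcome is ED or a PAED score of at least 12 at 10, 20 and 30 minutes. The cut-off differs from the definition, T=0 is left out, and ED is treated as something apart from the score.
- **When exposure and observation end.** Anesthetic Description: "The light will remain active and over the patient until the patient has been in the post anesthesia recovery unit (PACU) for 30 minutes". Risk/Discomfort: "The study will be terminated the moment the patient is awake and making purposeful eye contact with the PACU RN", with the lights ended at the same moment.

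**The concern.** The primary aim is a difference in the incidence of ED, so each child needs one yes/no status. The plan does not supply it.

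The missing-data sentence names two reasons for a missing score, one meaning no ED and the other meaning ED, and treats them alike. If a score above 12 was recorded before scoring stopped, nothing is lost. The problem is the child whose ED was recognised without such a score, for example between two scheduled times and then treated. Under the PAED definition that child is counted as no ED, or drops out if incomplete records are excluded.

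Even with complete scores, two analysts could reach different ED counts by using either nurse, both nurses or the mean, and any time or one time, with or without T=0. With few events expected, a handful of reclassified children matters, and a choice made after unblinding would leave the primary result open to selection.

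**Working it through.** **1. The plan's own figure.** Inputs from Sample size/Data Analysis: 40% against 15%, two-sided alpha 0.05, power 80%. Equal allocation is assumed. With pooled variance and p̄ = (0.40 + 0.15)/2 = 0.275:

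n per arm = [1.96·√(2·0.275·0.725) + 0.8416·√(0.40·0.60 + 0.15·0.85)]² / 0.25² = (1.238 + 0.510)² / 0.0625 ≈ 48.9, so 49 per arm and 98 in total. The stated N reproduces.

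Power = Φ[(d − 1.96·s0)/s1], where s0 = √(2p̄(1 − p̄)/n) and s1 = √([pC(1 − pC) + pB(1 − pB)]/n). At 49 per arm: (0.25 − 1.96·0.0902)/0.0866 = 0.845, giving 80.1%.

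Expected events: 49·0.40 + 49·0.15 = 19.6 + 7.35, about 27.

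**2. ED children with no recorded score above 12.** The documents give no share, so 10%, 20% and 30% are assumptions. Of 27 events, about 2.7, 5.4 or 8.1 would be affected at equal shares. With share m in an arm:

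- Counted as no ED: the observed rate is p(1 − m), with 49 per arm.
- Only these children dropped: the rate is p(1 − m)/(1 − pm), with arm size 49(1 − pm).

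| Unrecorded share, control / blue light | Counted as no ED: rates | Difference | Power | Dropped: difference | Power |
|---|---|---|---|---|---|
| 0 / 0 | 40% v 15% | 25.0 | 80% | 25.0 | 80% |
| 10% / 10% | 36% v 13.5% | 22.5 | 74% | 23.8 | 77% |
| 20% / 20% | 32% v 12% | 20.0 | 67% | 22.4 | 73% |
| 30% / 30% | 28% v 10.5% | 17.5 | 60% | 20.8 | 68% |
| 10% / 30% | 36% v 10.5% | 25.5 | 86% | 26.5 | 86% |
| 30% / 10% | 28% v 13.5% | 14.5 | 42% | 18.1 | 55% |

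The last two rows show that the direction depends on how the unrecorded share differs between arms. Where the difference widens, the higher figure for power reflects bias, not better information.

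The dropped columns remove ED children only. If children unscored because they woke were dropped too, at the same share in every group, the rates would stay at 40% and 15% and only the sample size would fall.

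**3. Raters and times.** The documents give no inter-rater agreement, so no size is attached to the missing two-nurse rule. On T=0, the lamp is lit at about the time of the first score ("On arrival to the PACU, the Drager phototherapy lamp will be illuminated over" the patient), so that score cannot reflect the light. Since "the patient will undergo routine deep extubation", many events on arrival are unlikely, and no figure is given for this either.

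**4. Which scores should exist.** One section keeps the light on to 30 minutes and schedules a score then; another ends both light and study once the child is awake with purposeful eye contact. Under the first, a child who wakes at 12 minutes still has scores due at 20 and 30 minutes; under the second, none. The passages contradict each other and must be reconciled.

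**The case against.** **The text partly answers the point.** Waking and ED can be read as known end states, so that nothing needs imputing, and the second model's outcome seems to treat ED as a recorded fact apart from the scores, which fits the nurse determination. This reading is reasonable but is not written down, and it conflicts with the only definition given, which is PAED above 12. The second outcome also has a different cut-off, leaves any versus all times open and ignores the second nurse.

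**A reader might infer that the gap must dilute the effect and cost power.** The documents do not support that. It follows only if the unrecorded shares are similar in the two arms. A light intended to raise alertness, combined with scoring that may stop on waking, gives no assurance that they are.

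**A reader might infer that the plan excludes unscored children.** It does not say so. Declining to impute scores is not the same as excluding children; dropping them is one possible reading.

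**A reader might infer that the plan has no primary test.** The plan assigns chi-square, or Fisher's exact test for small counts, to categorical variables and brings in logistic regression for adjustment. The unadjusted comparison is readily inferred and needs only confirming.

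**Conclusion.** The concern holds and should be fixed before unblinding. The plan sets a threshold but no complete rule for the primary outcome. It names two opposite reasons for missing scores without assigning either an ED status, gives the recorded nurse determination no role, and leaves the two nurses and four times uncombined. Conflicting text on when observation ends adds to the uncertainty over which scores exist.

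Missingness is related to outcome by the plan's own statement. The direction of bias in the treatment comparison cannot be determined from the documents. The power figures are illustrations: they assume 49 per arm, true rates of 40% and 15%, and unrecorded shares that the documents do not give. The sample size calculation itself has no arithmetic error.

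**What to change.** Before unblinding, amend the analysis plan as follows.

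1. **Primary endpoint.** ED = yes if PAED is above 12 at any of 10, 20 or 30 minutes under one pre-specified two-nurse rule (for example the mean, or the single available score if one is missing), **or** if the blinded nurse determination documents ED after arrival, whether or not any score is missing. Making the nurse criterion unconditional matters: if it applied only when a score was missing, missingness would decide the outcome, and a fully scored child with ED between scheduled times would still be missed.
2. **Everyone else.** All other randomized children, including those unscored because awake, are ED = no. All randomized children stay in the analysis.
3. **Disagreement.** State how conflicting determinations by the two nurses are resolved.
4. **T=0.** Report it by arm as a score taken as the lamp is lit, not as a primary event.
5. **Sensitivity analyses.** (a) PAED scores above 12 only; (b) excluding children with ED at T=0; (c) counting as ED = yes those with missing scores who were not documented awake and had no nurse-determined ED.
6. **Cut-off and test.** Use one cut-off throughout, or label the composite using at least 12 as supportive. Confirm that the unadjusted chi-square/Fisher comparison is primary.
7. **Reconcile** Anesthetic Description and Postoperative evaluation with Risk/Discomfort on when the light and scoring end.

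The cost is mainly wording, since PAED scores and the nurse determination are already to be recorded. The score sheet should also show why a score is missing and whether a nurse-determined ED arose after arrival. The downside is that blinded nurse judgement decides some primary outcomes, and the 40% rate and 80% power may need restating if they rest on a PAED-only definition.

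### Nurse-clustered standard errors in the two adjusted ED models: nurse count and small-sample correction are unstated, and with few nurses the treatment test exceeds its 5% error rate

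*Combined protocol and SAP*

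**What the plan says.** The Statistical Analysis Plan (Sample size/Data Analysis) specifies two logistic models, one for ED and one for a broader outcome that adds PAED scores of 12 or more. On covariates: "Both regression models used as independent predictors the following variables: treatment group, age, weight, gender, and ASA category". On standard errors: "Robust standard errors were derived to account for any within-cluster correlation at the individual nurse level". The reason given is "given the possible serial correlation of outcomes within each nurse caring for his or her patients". On significance: "All p-values < 0.05 were considered statistically significant".

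The section does not give the number of nurses, a small-sample correction, the reference distribution for the test, or the row structure of the models.

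The Randomization section allocates each patient individually. It also says: "Patients will be evaluated for emergence delirium by two nurses blinded to the study arm". The section on postoperative evaluation repeats that two blinded PACU nurses score each child. The SAP's phrase about a nurse and his or her patients can fairly be read as one assigned nurse per child. If the cluster is instead one of the two raters, the SAP does not say which.

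**The concern.** Clustered (sandwich) errors are justified by having many clusters. With few, the variance estimate is on average too small and also unstable, so comparing the statistic with a normal distribution rejects too often. The SAP chose a method whose validity depends on a number that it never gives.

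The clustering is also not needed for this purpose. Treatment is assigned child by child, so both arms can occur among any nurse's patients. A nurse who tends to score high raises scores in both arms and does not systematically favour either.

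At stake are the adjusted odds ratio's confidence interval and p-value, judged against 0.05. An analysis meant to support the main comparison could look more certain than it is.

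**Working it through.** **Inputs from the documents.** ED 40% against 15%; two-sided alpha 0.05; 80% power; 98 participants; individual randomisation; treatment plus age, weight, gender and ASA category in each model.

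**Assumptions not in the documents.** 1:1 allocation; 6 to 40 nurses; one row per child; between-nurse SD of 0, 0.6 or 1.0 on the logit scale; equal or uneven caseloads; covariate distributions.

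**Step 1. The plan's own figure.** Pooled-variance formula, mean rate (0.40 + 0.15)/2 = 0.275:

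- 1.960 × √(2 × 0.275 × 0.725) = 1.238
- 0.8416 × √(0.40 × 0.60 + 0.15 × 0.85) = 0.510
- n per arm = (1.238 + 0.510)² / 0.25² = 48.9, so 49 per arm and 98 in total.

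The stated sample size reproduces. It does not depend on the nurse-clustered error.

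**Step 2. What to expect with few clusters.** With equal caseloads, the statistic scaled by G/(G-1) behaves roughly like t on G-1 degrees of freedom. Comparing it with 1.96 then has error P(|t| > 1.96):

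- G = 6: 10.7%
- G = 10: 8.2%
- G = 20: 6.5%
- G = 30: 6.0%
- G = 40: 5.7%

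Without the scaling, the effective cut-off is 1.96 × √((G-1)/G). That is 1.789 at G = 6 (error 13.4%) and 1.859 at G = 10 (error 9.6%).

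**Step 3. Simulation of the adjusted model under no treatment effect.** 98 children, one row each, ED 27.5% (40% also tried), 4,000 trials per setting. The Monte Carlo standard error is √(0.05 × 0.95/4000) = 0.3 points, rising to 0.6 at 15%. Ranges run over the nurse SDs and caseloads tried.

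| Nurses | Model-based | Clustered, z, no scaling | Clustered, z, G/(G-1) | Clustered, G/(G-1), t on G-1 df |
|---|---|---|---|---|
| 6 | 4.8-6.0% | 12.9-17.0% | 10.7-14.2% | 5.0-7.1% |
| 10 | 4.6-5.8% | 9.5-12.6% | 7.9-10.9% | 4.4-7.1% |
| 20 | 4.4-6.0% | 6.6-8.8% | 6.1-7.9% | 4.6-5.8% |
| 30 | 4.8-6.1% | 6.2-7.8% | 5.6-7.3% | 4.6-6.1% |

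The low end of each clustered z range matches step 2, and uneven caseloads generally give the high end at 6 and 10 nurses. Repeat simulations agree within about 1 point: with scaling, 11-15% (6 nurses), 8-11% (10), 7-8% (20) and 6-7% (30-40); without scaling, about 13-18% (6) and 10-12% (10).

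**Step 4. Power at 40% against 15%** (nurse SD 0-0.6). Model-based 78-81%; clustered z with G/(G-1) 77-81%. Clustering gains nothing. With the t reference, power is 59-64% at 6 nurses and 67-72% at 10.

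**Step 5. Where model-based errors stop working.**

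- *Both ratings as separate rows* (assumed patient SD 3; 2,000 trials per setting; 6 to 30 nurses): model-based error is 10-12%. Nurse clustering does not cure this: 13-19% with z and G/(G-1), and 10-12% with the t reference.
- *Treatment effect varying by nurse* (assumed SD 0.6): model-based 8.6%, 6.7% and 5.4% with 6, 10 and 30 nurses; clustered z with G/(G-1) 12.2%, 9.0% and 5.3%; with the t reference 5.2%, 4.8% and 4.4%.

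**The case against.** The strongest reply is that the harm rests on a nurse count that the documents do not contain. A reader might infer that the unit had about ten nurses or fewer. Nothing says so: two nurses per child is not a total, and with 30 to 40 nurses the excess is only a point or two. This stands, so the point must be conditional.

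A reader might also infer from the SAP's silence that no correction was used. It does not show that; software may apply part of one by default. But G/(G-1) scaling alone leaves 11-15% at 6 nurses, so such a default would not settle the matter.

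Nor can one say that this trial's adjusted p-value is too small. The clustered interval (with that scaling) was narrower than the model-based one in only about 52-69% of simulated trials.

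That model-based errors are enough in general is also too strong. It depends on one row per child, which the SAP does not state, although it mentions three scoring times and each child has two raters. It weakens if the effect differs by nurse. The documents give no reason to expect that, since the nurses are blinded; even in that simulation, the clustered z-test was further from 5% with 6 or 10 nurses.

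Finally, the SAP is partly in the past tense. If the models have been run, replacing one error with another afterwards would itself be a post hoc choice. That stands and shapes the fix.

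**Conclusion.** The concern holds in conditional form. As written, a reader cannot tell whether the adjusted treatment test keeps its 5% level. Assuming one row per child, a normal reference and G/(G-1) scaling, error is roughly two to three times nominal with 6 nurses, about 1.6 to 2.2 times with 10 (8-11% over 5%), and close to nominal with 30 or more. Model-based errors stay at about 4.5-6% at every count tried, given one row per child and a treatment effect that does not vary by nurse.

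The documents do not support reading this as a fault in the whole analysis: the chi-square/Fisher comparison and the sample size of 98 are untouched. The change is worth making because it is cheap and does not depend on knowing the nurse count. Confidence is medium, because the nurse count, caseloads and between-nurse variation are all assumed.

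**What to change.** Suggested SAP wording: *Each child contributes one row to each adjusted model. The treatment odds ratio, 95% confidence interval and p-value use ordinary model-based standard errors. As a sensitivity analysis, standard errors are clustered on nurse; the report states the number of nurses and which nurse defines the cluster, and uses a small-sample correction with a t reference on (nurses - 1) degrees of freedom.*

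If both nurses' ratings or several time points are meant to enter as separate rows, model-based errors are not valid. Dependence within the child must then be handled explicitly. If the models have already been run, report both errors side by side rather than switching.

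This change should leave the ED definition, the combining of the two ratings and the choice of time points alone. They are endpoint questions, and new wording there would have to fit the SAP's rule on missing PAED scores.

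Cost: wording only, with no new patients or assessments. Nurse identity is needed only for the sensitivity analysis. There are three downsides. The reported interval will often be slightly wider. Model-based error runs somewhat above 5% if the effect varies by nurse and nurses are few. The t reference cuts the sensitivity analysis's power to about 60% with 6 nurses and 68% with 10, and leaves error up to about 7% with uneven caseloads, so it should not be the main analysis.
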